9.0 STATISTICAL CONSIDERATIONS

9.1 Statistical Hypotheses

The aim of this study is to show superiority of ensifentrine over placebo regarding selected efficacy measures. The null hypothesis to be tested for each endpoint will be that there is no difference between ensifentrine and placebo, against the alternative hypothesis that ensifentrine is better than placebo. All tests will be two-sided at a 5% significance level. Primary and key secondary endpoints used for claims will be tested in a sequential order to preserve the alpha level. Testing will stop once a not significant result is achieved. Test order will be FEV₁ AUC_{0-12h} at 12 weeks, peak FEV₁ at 12 weeks, weekly mean E-RS total symptom score at week 24, SGRQ total score at Week 24, morning trough FEV₁ at Week 12, FEV₁ AUC_{0-4h} at 12 weeks and proportion of SGRQ responders at 24 weeks.

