9.2 Sample Size Determination

Approximately 800 patients will be randomized. The standard deviation for the change in FEV₁ AUC_{0-12h} is estimated to be 250 mL. With a 2-sided test at a 5% significance level and 500 vs. 300 evaluable patients in the two groups, there will be an 90% power to detect a true difference of 59 mL between the treatments. If the withdrawal rate at 24 weeks exceeds 25% overall, additional patients may be randomized to the study to compensate for the loss of data.

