9.4.4 Missing Data

All data collected after treatment withdrawal will be used in the analyses. Patients withdrawn from study will perform an End-of-Study visit after decision to withdraw the patient has been made. Data collected at such visits will be used for analysis even if outside the visit window for the endpoint. Remaining missing data will primarily be imputed using multiple imputation based on baseline characteristics and data collected at post-randomization visits. In addition, a worst-case scenario using the average change in the opposite treatment group will be used for imputation as a sensitivity analysis. For the responder analysis of SGRQ, patients with no available data for imputation will be considered non-responders as a sensitivity analysis. In exacerbation analyses, patients are included with data collected up to last day in the treatment period/period of recording following treatment withdrawal.

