
Secondary
	
To evaluate the effect of ensifentrine on COPD symptoms.
	
Patients with moderate to severe COPD aged 40-80 years (inclusive) that are in the mITT population. See full list of inclusion and exclusion criteria in sections 5.1, 5.2 and 5.3 of study protocol.
	
Change from baseline (i.e. mean over the last 7 days of run-in) to the mean weekly value at Week 24 in COPD symptoms, as measured by daily diary (Evaluating Respiratory Symptoms for COPD [E-RS™;COPD])
	
Regardless of whether the patient discontinues treatment prematurely and regardless of major protocol deviation, as per the Treatment Policy strategy.
	
Estimated treatment difference at the end of the double-blind period (and corresponding 95% CI) from ANCOVA analysis.

Secondary
	
To evaluate the effect of ensifentrine on health-related quality of life.
	
Patients with moderate to severe COPD aged 40-80 years (inclusive) that are in the mITT population. See full list of inclusion and exclusion criteria in sections 5.1, 5.2 and 5.3 of study protocol.
	
1. Change from baseline in the St. George's Respiratory Questionnaire (SGRQ) total score at Week 24 2. Proportion of SGRQ responders at Week 24
	
Regardless of whether the patient discontinues treatment prematurely and regardless of major protocol deviation, as per the Treatment Policy strategy.
	
1. Estimated treatment difference at the end of the double-blind period (and corresponding 95% CI) from ANCOVA analysis. 2. Odds ratio for proportion of responders with an improvement of at least 4 units at the end of the double-blind period (and corresponding 95% CI) from logistic

[figure not shown]
						regression analysis.
--	--	--	--	--	--	----------------------

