- Sections 9.4.1 and 9.4.4 in the protocol states, “A sensitivity analysis [on the proportion of responders on the SGRQ] will be performed in which patients with missing data at the required visit will be considered non-responder in the analysis”, and “For the responder analysis of SGRQ, patients with no available data for imputation will be considered non-responders as a sensitivity analysis”, respectively. However, a non-responder analysis may create an unintentional bias in favour of the treatment arm. I.e. if placebo patients discontinue, this technique may inadvertently set more values in the placebo arm to “non-responder”. Therefore, this technique for missing data analysis will not be implemented.
- Analysis of E-RS total score responder, defined as a decrease from baseline in the week mean total of E-RS score of greater than or equal to 2, added in the Section 16.3.1.7.
- Analysis of Morning trough FEV₁ responder, defined as an improvement from baseline of 100 mL or more, added in the Section 16.3.1.8.
- Chronicity section removed from Adverse Events section.
- A sensitivity analysis will be performed for weekly mean E-RS total score, using ANCOVA approach, as described in section 16.2.4 of the SAP, in which all patients with baseline mean = 0 will be excluded.
- Due to the unreliability of the data, site [REDACTED] will be removed from efficacy and safety analyses in any section.
- Extended randomized, extended mITT and extended Safety populations set will be included as new populations to manage this site to be removed. Added in the Section 5.

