16.2.2.2. MI method – binary data

For the analyses of proportion of SGRQ, weekly mean total E-RS and Morning trough FEV₁ responders, an analysis will be performed using MI based on the missing data assumption MAR. This process will impute the continuous underlying data, as per 16.2.2.1 (morning trough FEV₁, SGRQ total score and weekly mean total E-RS), and then recalculate the binary outcome of responder or non-responder. The analysis will follow the steps below (Ratitch and O’Kelly, 2014, pp.124 - 127) (below the example uses morning trough FEV₁, but it is repeated also for other endpoints mentioned above):

- 1) Follow steps 1 and 2 from 16.2.2.1 for the continuous morning trough FEV₁ results.
- 2) For the imputed results re-calculate response, where a response is an improvement from baseline in morning trough FEV₁ of 100 mL.
- 3) Analyse each multiply imputed dataset separately, as described in section 16.2.3 of the SAP, producing LS Means, odd ratios and corresponding 95% confidence interval and p-value.
- 4) For the odds ratios:
 - a) Before applying Rubin’s rule, apply a normalising transformation to the odds ratios as well as their standard errors. The distribution of the log of odds ratios approximates to a normal distribution. Therefore, calculate the transformed values, where OR is odds ratio, Lower/Upper CL are the confidence interval estimates of the ORs:

$$OR_{norm} = \log(OR)$$

$$SE_{norm} = \frac{(\log(Upper\ CL) - \log(Lower\ CL))}{(2 \times 1.96)}$$

- b) Apply Rubin’s rule with PROC MIANALYZE to the transformed odds ratios with corresponding transformed standard errors.
- c) Back-transform the combined results as follows:

$$OR_{bt} = \exp^{OR_{norm}}$$

$$Lower\ CL_{bt} = OR_{bt} \times e^{(-1.96 \times SE_{norm})}$$

$$Upper\ CL_{bt} = OR_{bt} \times e^{(1.96 \times SE_{norm})}$$

- 5) For the odds of response per treatment arm
 - a) Take the LS means to be estimates of the log-odds of response per treatment arm and assume that they asymptotically tend to a normal distributions.

- b) Apply Rubin's rule with PROC MIANALYZE to the LS means.
- c) Transform the combined results by exponentiating to get the odds of response per treatment arm.

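### Death has no estimand strategy, and missing SGRQ scores are imputed under MAR before response is classified, so a patient who dies before Week 24 can count as a responder in part of the imputed datasets

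*SAP*

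**What the plan says.** **Estimands.** SAP 2.5, Table 1, handles intercurrent events identically in every row, including the health-related quality of life row that holds the Week 24 SGRQ responder proportion: "Regardless of whether the patient discontinues treatment prematurely and regardless of major protocol deviation, as per the Treatment Policy strategy". Death is not named.

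**Imputation.** SAP 7.3 uses all data collected on or off treatment and at end-of-study visits, then passes every remaining missing mITT value to the imputation sections. For responders, 16.2.2.2 imputes the underlying continuous score under MAR (100 imputations, 16.2.2.1) "and then recalculate the binary outcome of responder or non-responder". The same procedure covers the E-RS and morning trough FEV1 responders. The SGRQ responder analysis in 16.2.3.2 cites 16.2.2.3 instead, which is the same MAR imputation with minimum and maximum limits. Sections 16.3.2 and 16.3.3 also cite 16.2.2.3 for responder analyses. None of these sections makes an exception for death.

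**Sensitivity analyses.** Protocol 9.4.4 planned: "For the responder analysis of SGRQ, patients with no available data for imputation will be considered non-responders as a sensitivity analysis". SAP 3.3 removes this because scoring placebo dropouts as failures could favour the active arm: "Therefore, this technique for missing data analysis will not be implemented". SAP 16.2.2.4 and 16.2.4 keep average imputation and a tipping-point analysis for the key secondary endpoints.

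**Role of the endpoint.** SGRQ responders at Week 24 is the last of seven endpoints in the SAP 7.4 hierarchy. Protocol 9.1 states: "All tests will be two-sided at a 5% significance level".

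**The concern.** Treatment policy means using the value observed whatever happened earlier. That works after stopping the drug or after a protocol deviation. After death there is no value, so the strategy is undefined and the imputation section decides by default. Its default is to simulate the score the patient might have had if alive, then ask whether that score improved by at least 4 units.

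For a continuous score the meaning of a value after death can be debated. For a binary responder endpoint it is hard to defend: a patient who died before Week 24 did not respond at Week 24, yet the plan gives that patient partial credit as a responder. The reason SAP 3.3 gives for dropping the non-responder analysis concerns patients who discontinue. It is a fair argument against failing every dropout, but not a reason to simulate a response for a patient whose outcome is known.

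At stake is an alpha-controlled endpoint. If deaths differ between arms beyond the 5:3 allocation, the arm with relatively more deaths looks better than it should.

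**Working it through.** **1. The plan's own figure.** The only stated power figure concerns the primary endpoint. The SD "is estimated to be 250 mL", with "500 vs. 300 evaluable patients in the two groups" and "90% power to detect a true difference of 59 mL between the treatments". SE = 250 × √(1/500 + 1/300) = 18.26 mL; 59/18.26 = 3.232; 3.232 − 1.960 = 1.272; Φ(1.272) = 0.898. The stated 90% reproduces. The documents give no response rate, power or expected deaths for the SGRQ responder endpoint, so everything numerical below is assumed apart from the 500 and 300.

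**2. Tracing a death through the rules.** A patient is dosed (so in the mITT), dies before Week 24 and has no score that SAP 6.4 windows to Week 24. Table 1 gives no strategy. SAP 7.3 classes the Week 24 score as a remaining missing value. Under 16.2.2.2, or 16.2.2.3 if the reference in 16.2.3.2 is followed, a score is drawn in each of 100 datasets and classified. The results are pooled by Rubin's rules.

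**3. Chance that one draw is a responder.** The imputation conditions on treatment, region, strata, the patient's baseline and the scheduled visits available. Assume a conditional mean change μ between 0 and −6 and a residual SD σ between 10 and 16. Then P(responder) = Φ((−4 − μ)/σ):
- μ = 0, σ = 10: Φ(−0.40) = 0.345
- μ = 0, σ = 16: Φ(−0.25) = 0.401
- μ = −6, σ = 10: Φ(0.20) = 0.579
- μ = −6, σ = 16: Φ(0.125) = 0.550

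So each draw is a responder with probability of about 0.35 to 0.58. A patient already deteriorating on SGRQ would have a lower probability.

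**4. Effect on the odds ratio.** As a rough stand-in, give each deceased patient the arm's response rate under the plan and zero under the alternative. With response rates pE and pP and deaths dE and dP, the responder counts with death as non-response are a = pE(500 − dE) and c = pP(300 − dP). OR = a(300 − c)/[c(500 − a)], and the SE of log OR is √(1/a + 1/(500 − a) + 1/c + 1/(300 − c)), unadjusted.

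Under the plan at 45% vs 38%: 225/500 vs 114/300, OR = (225 × 186)/(275 × 114) = 1.335, SE 0.149, z = 1.94, p = 0.053.

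For 5 vs 3 deaths: a = 0.45 × 495 = 222.75, c = 0.38 × 297 = 112.86, OR = (222.75 × 187.14)/(277.25 × 112.86) = 1.332.

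| Deaths (ensifentrine vs placebo) | 45% vs 38%: OR, p | 50% vs 40%: OR, p | 55% vs 45%: OR, p |
|---|---|---|---|
| As planned (deaths imputed) | 1.335, 0.053 | 1.500, 0.0061 | 1.494, 0.0063 |
| 5 vs 3 (proportional to 5:3) | 1.332, 0.055 | 1.495, 0.0066 | 1.488, 0.0068 |
| 1 vs 3 | 1.352, 0.044 | 1.519, 0.0048 | 1.515, 0.0047 |
| 5 vs 1 | 1.318, 0.064 | 1.479, 0.0082 | 1.470, 0.0087 |
| 8 vs 1 | 1.304, 0.076 | 1.461, 0.0104 | 1.451, 0.0113 |

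Proportional deaths barely move the estimate. Imbalanced deaths move it in either direction. In this table the significance verdict changes only in the first column, which starts at the boundary, and only for 1 vs 3 deaths, where it moves towards ensifentrine.

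**The case against.** Four points weigh on the other side.

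- **Other missing-data analyses exist.** A reader might infer that nothing tests the MAR assumption. The documents do not support that. SAP 16.2.2.4 and 16.2.4 apply average imputation and an MNAR tipping point to the key secondary endpoints, and a deceased patient's imputed value would be among those shifted. What remains is narrower: neither method isolates death or sets it to failure. Both are described as ANCOVA methods, and 16.2.4 places its analyses at Week 12, so their use for a Week 24 binary endpoint is unclear.
- **The imputation is conditional.** A reader might infer that each death is scored as a full success, or at the arm's response rate. Neither is right. Each death is a responder in a fraction of the 100 datasets, and the model uses the patient's own baseline and visits. The arm rate in step 4 is a simplification.
- **The effect is small and has no fixed direction.** A reader might infer a bias towards ensifentrine. Nothing in the documents indicates which arm would have more deaths. The endpoint is last in the hierarchy, so no later test depends on it. This stands, and it limits the weight of the point.
- **Deaths may be incompletely known.** The SAP identifies deaths through adverse events with a fatal outcome (17.1.4). Protocol Appendix 7 gives death from disease progression as an example that may fall outside the SAE definition. Protocol 8.7.1 does not oblige investigators to seek events after participation ends. So it cannot be assumed that every death date is available.

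The continuous SGRQ and E-RS endpoints, fourth and third in the hierarchy, also lack a strategy for death. Scoring death as non-response has no direct counterpart there, so this point is confined to the responder analyses.

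**Conclusion.** The point holds. Followed as written, the plan gives patients who die before Week 24 without a usable score a simulated SGRQ response in an alpha-controlled endpoint. This follows from the rules themselves and does not depend on the illustration. Its likely size is modest: close to nothing if deaths are few and proportional to allocation (OR 1.335 to about 1.332 for 5 vs 3), and up to about 0.03 on the odds ratio for 8 vs 1 deaths at 45% vs 38%. It could change a conclusion only near p = 0.05. Response rates, deaths, and the conditional means and SDs are assumptions. It is worth correcting because the rule is wrong for a binary outcome and cheap to change, and because the choice should be made before anyone knows which arm had more deaths.

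**What to change.** Before unblinding:

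1. In SAP Table 1, add death as a separate intercurrent event for the SGRQ responder endpoint, with a composite strategy in which death before the assessment is non-response.
2. In 16.2.2.2, and wherever 16.2.3.2, 16.3.2 and 16.3.3 cite 16.2.2.3 for responders, add a step after response is recalculated: patients known to have died before the assessment are non-responders in every imputed dataset.
3. Apply the same step to the E-RS and morning trough FEV1 responder analyses in section 16.3. These are not in Table 1, so a row there does not reach them.
4. Reconcile the cross-references between 16.2.2.2 and 16.2.2.3, so that each responder analysis names one imputation method.
5. Identify deaths from all recorded sources, including fatal adverse events and disposition.

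Leave imputation of other missing responder data as planned, so the dropout bias that SAP 3.3 wanted to avoid is not brought back.

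The cost is a short SAP amendment, a derived death indicator and one added step in each responder program. Responder rates fall slightly in each arm, and deaths after loss to follow-up may stay unknown and continue to be imputed.

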3. STUDY DESIGN

3.1. GENERAL DESCRIPTION

This is a Phase III, multicenter, randomized, double-blind, parallel group, placebo-controlled study. A flow chart illustrating the key components of the study is provided in Figure 1:

Figure 1: Study Flow Chart

Approximately 800 patients with moderate to severe COPD aged 40 to 80 years (inclusive) will be stratified by two different factors: stable background maintenance long-acting muscarinic antagonist (LAMA) or long-acting beta-2 agonist (LABA) therapy use (yes or no) and cigarette smoking (current or former), then randomized 5:3 to receive ensifentrine (3 mg): placebo for 24 weeks. The background therapy strata will be capped at 50%. Up to 20% of patients are allowed to take inhaled corticosteroids during the study under certain provisions, as detailed in the sections 6.7.2 and 6.7.3 of the study protocol. Patients in the background maintenance LAMA or LABA therapy strata must withhold twice-daily maintenance LAMA or LABA (or LAMA/ICS or LABA/ICS) for 24 hours and once-daily maintenance LAMA or LABA (or LAMA/ICS or LABA/ICS) for 48 hours prior to initiation of any spirometry. All patients must withhold short-acting beta-2 agonist (SABA) rescue medication for at least 4 hours prior to initiation of any spirometry.

Patients are expected to take the study medication twice daily, administered via a standard jet nebulizer, during the study period. Schedule of in-clinic dosing can be found in section 1.4 of the study protocol.

3.2.SCHEDULE OF EVENTS

Schedule of activities can be found in section 1.3 of the study protocol.

3.3.CHANGES TO ANALYSIS FROM PROTOCOL

Changes to analysis from protocol include:

- “COPD severity” added as a subgroup analysis.
- Per-protocol population definition updated to exclude patients that discontinued study medication before study day 74.
- Sections 9.4.1 and 9.4.4 in the protocol states, “A sensitivity analysis [on the proportion of responders on the SGRQ] will be performed in which patients with missing data at the required visit will be considered non-responder in the analysis”, and “For the responder analysis of SGRQ, patients with no available data for imputation will be considered non-responders as a sensitivity analysis”, respectively. However, a non-responder analysis may create an unintentional bias in favour of the treatment arm. I.e. if placebo patients discontinue, this technique may inadvertently set more values in the placebo arm to “non-responder”. Therefore, this technique for missing data analysis will not be implemented.
- Analysis of E-RS total score responder, defined as a decrease from baseline in the week mean total of E-RS score of greater than or equal to 2, added in the Section 16.3.1.7.
- Analysis of Morning trough FEV₁ responder, defined as an improvement from baseline of 100 mL or more, added in the Section 16.3.1.8.
- Chronicity section removed from Adverse Events section.
- A sensitivity analysis will be performed for weekly mean E-RS total score, using ANCOVA approach, as described in section 16.2.4 of the SAP, in which all patients with baseline mean = 0 will be excluded.
- Due to the unreliability of the data, site [REDACTED] will be removed from efficacy and safety analyses in any section.
- Extended randomized, extended mITT and extended Safety populations set will be included as new populations to manage this site to be removed. Added in the Section 5.

4. PLANNED ANALYSES

A final analysis after DBL is planned for this study.

4.1.DATA MONITORING COMMITTEE (DMC)

There will be no DMC for this study.

4.2. INTERIM ANALYSIS

There is no interim analysis planned for this study, however additional patients may be randomized if:

- the SD has increased significantly from the estimated 250 mL, as per sponsor discretion, and/or
- the withdrawal rate at 24 weeks exceeds 25% overall, and the percentage of patients with missing FEV₁ over 12 hours at Week 12 in mITT (modified Intent-to-Treat) population exceeds 20% overall.

Note: As part of the primary endpoint analysis, SD of the treatment difference is calculated to check the sample size with 90% power.

4.3. FINAL ANALYSIS

All final, planned analyses identified in this SAP will be performed by IQVIA Biostatistics following sponsor authorization of SAP (and associated output shells), DBL, analysis sets and unblinding of treatment.

The population PK analysis identified in the protocol will be performed separately by the assigned Verona Pharma Designee. A separate modeling data analysis plan will be prepared for the analyses and results will be reported separately from the clinical study report.

5. ANALYSIS SETS

Agreement and authorization of patients included/excluded from each analysis set will be conducted prior to the unblinding of the study. For PK set see sections 5.10 and 20 of the SAP. Analyses will be performed for the analysis sets described in Table 2.

Table 2: Analysis sets

	All Patients Enrolled Set	All Patients Random. Set	Extended Random. Set	Modified Intent-to-Treat Pop.	Extended modified Intent-to-Treat Pop.	Per-Protocol Pop.	Safety Set	Extended Safety Set	PK Set
Disposition of patients	X	X	X						

Protocol deviations		X							
Demographic and other baseline characteristics		X	X	X					
Surgical and medical history							X		
Prior and concomitant medication							X		
Compliance							X		
Efficacy: Primary endpoint				X	X	X			
Efficacy: Secondary endpoints				X	X	X			
Efficacy: Other endpoints				X	X				
Sensitivity Analyses				X	X	X			
Safety							X	X	
Pharmacokinetics									X

5.1.PROCESS FOR ANALYSIS SET ASSIGNMENT

Analysis set assignments and any associated reasons for analyses set exclusion will be described in the BDR plan and finalized within the BDR report prior to unblinding.

5.2.ALL PATIENTS ENROLLED SET

The all patients enrolled (ENR) set will contain all patients who provide informed consent for

this study. Patients will be classified according to randomized treatment with patients not randomized presented in a separate category, see APPENDIX 1.

5.3. ALL PATIENTS RANDOMIZED SET

The all patients randomized (RND) set will contain all patients in the ENR set who were randomized to study medication. For analyses and displays based on RND, patients will be classified according to randomized treatment. Site number [REDACTED] will be excluded from this population.

